3.1. Study Rationale

Psoriasis (Ps) is a common chronic skin disorder with an estimated prevalence of 1.0% in Japan (Tang et al. 2014). The pathogenesis of psoriasis has undergone many paradigm shifts during the past 3 decades. Psoriasis is no longer considered fundamentally a skin disease, but rather a chronic inflammatory process resulting from a dysfunctional immune system (Kim and Krueger 2015). For patients with psoriasis, the protective elements of the skin (corneocytes, keratinocytes, chemokines, and immunocytes, such as T cells and dendritic antigen-presenting cells [DiMeglio et al. 2011; Bergboer et al. 2012]) become disrupted, resulting in dysfunctional feedback loops and vicious cycles leading to development of life-long, thick, scaly, well-demarcated plaques (DiMeglio et al. 2014). Psoriasis includes several phenotypes often separated into the following classifications; plaque Ps, guttate Ps, pustular Ps, and erythrodermic Ps (EP). Psoriatic arthritis (PsA) may coexist in up to 30% of patients with Ps. The most common type of psoriasis is plaque Ps (psoriasis vulgaris), and clinical features include sharply demarcated, scaly erythematous plaques that are often associated with itching, pain, and cracking of the skin. These lesions most typically affect the elbows, knees, scalp, lumbar area, umbilical area, and gluteal cleft. Approximately 1/4 to 1/3 of plaque Ps patients have moderate-to-severe Ps, corresponding to involvement of over 5% of their body surface area (BSA) (Dubin et al. 2003; Menter and Griffiths 2007). Disease of this extent is physically and/or socially debilitating to a degree comparable with other chronic medical conditions (Rapp et al. 1999).

3.2. Background

Ixekizumab (LY2439821, Taltz®) is a humanized immunoglobulin G subclass 4 (IgG4) monoclonal antibody (MAb) that binds with high affinity and specificity to interleukin (IL)-17A,

a proinflammatory cytokine. Ixekizumab does not bind to ligands IL-17B, IL-17C, IL-17D, IL-17E, or IL-17F.

Phase 3 clinical studies show that ixekizumab is efficacious and has an acceptable safety profile for the treatment of adult patients with moderate-to-severe Ps and for adult patients with active PsA. Ixekizumab was approved in Japan for the treatment of Ps, PsA, EP, and GPP at an initial dose of ixekizumab 160 mg followed by ixekizumab 80 mg administered Q2W from Week 2 through Week 12, and thereafter 80 mg Q4W. In August 2018, a new dosage and administration was approved in Japan to support 80mg Q2W continued dosing beyond Week 12 for patients with Ps, PsA, EP and GPP who have an inadequate response at Week 12. However, clinical studies consisting of the main data package in this new approval did not include the data from patients with EP and GPP who underwent treatment of ixekizumab 80 mg Q2W over 12 weeks. Therefore, the PMDA agreed that Eli Lilly Japan would conduct a study to evaluate the use of ixekizumab Q2W dosing beyond Week 12 in patients with EP and GPP in order to provide support for consistent dosing guidelines for the treatment of all indications (ie, Ps, PsA, EP, and GPP) with ixekizumab.

3.3. Benefit/Risk Assessment

Continued 80 mg Q2W dosing of ixekizumab was shown to be more efficacious over 52 weeks of treatment compared with continuous Q4W dosing in moderate-to-severe plaque psoriasis patients (Langley et al. 2018). Clinically meaningful benefit from continued Q2W dosing beyond Week 12 was prominent in moderate-to-severe plaque psoriasis patients who had inadequate response at Week 12. Although there are no data available for efficacy of ixekizumab Q2W dosing beyond 12 weeks in EP and GPP patients, the long term efficacy data in plaque psoriasis patients are suggestive of the incremental efficacy of ixekizumab with continued Q2W dosing in EP and GPP patients who have an inadequate response at Week 12, over the initially approved dosing regimen.

Safety profiles in plaque psoriasis patients who received ixekizumab Q2W over 52 weeks were comparable to those in Q4W treatment groups, with no unexpected safety signals observed. Meanwhile, no serious adverse events (SAEs) or adverse events (AEs) leading to treatment discontinuation were reported from EP and GPP patients who received ixekizumab via the initially approved dosing regimen. Also, overall safety profiles were comparable between EP and GPP patients and psoriasis patients.

Given the expected clinical benefit, potential risks derived from continued Q2W dosing may be acceptable in EP and GPP patients.

More information about the known and expected benefits, risks, SAEs and reasonably anticipated AEs of ixekizumab are to be found in the Investigator's Brochure (IB).

4. Objectives and Endpoints

Table RHCV.2 shows the objectives and endpoints of the study.

Table RHCV.2. Objectives and Endpoints

| Objectives | Endpoints |
|---|---|
| 
Primary
 
 To assess the efficacy of ixekizumab Q2W beyond Week 12 in patients with generalized pustular psoriasis (GPP) and erythrodermic psoriasis (EP) | 
 Number of patients who improved Global Improvement Score (GIS) at least 1 point from Week 12 through Week 20 and with ≤ 2 of GIS |
| Objectives and Endpoints | |
| Objectives | Endpoints |
| 
Secondary
 
 To assess the efficacy of ixekizumab Q2W beyond Week 12 in patients with GPP and EP To assess the health outcomes of ixekizumab Q2W beyond Week 12 in patients with GPP and EP To evaluate the potential development of anti-ixekizumab antibodies of ixekizumab Q2W beyond Week 12 in patients with GPP and EP | 
The following endpoints will be assessed at each scheduled visit after Week 12:
 
 Number of patients with each GIS grade (1: Resolved, 2: Improved, 3: Unchanged, 4: Worsened) Number of patients who achieved sPGA (0, 1) and sPGA (0) Number of patients who achieved PASI 75, PASI 90, and PASI 100 from baseline Change from baseline, and percent improvement from baseline in PASI Change from baseline in PSSI in patients with scalp involvement at baseline, and percent of BSA involvement of Psoriasis Change from baseline in DLQI total score and domains, and Itch NRS score Number of patients who achieved DLQI (0, 1) and DLQI (0) Number of patients who achieved Itch NRS ≥ 4 point reduction from baseline for patients who had baseline Itch NRS ≥ 4 Number of patients who developed treatment-emergent anti-ixekizumab antibody (TE-ADA) and neutralizing anti-ixekizumab antibody (NAb) 
GPP ONLY
 
 Change from baseline on assessment of Generalized Pustular Psoriasis Severity Index at Week 12 and Week 20/ETV. |

Note: Global improvement scores will be assessed in the four grades by comparing the psoriatic findings: (1) resolved, (2) improved, (3) unchanged, and (4) worsened. The global improvement score is assessed based on the comparison of the psoriatic findings, sPGA, PASI score, and other evaluations with those at the baseline.

Abbreviations: BSA = body surface area; DLQI = Dermatology Life Quality Index; EP = erythrodermic psoriasis; GIS = Global Improvement Score; GPP = generalized pustular psoriasis; NAb = neutralizing anti-ixekizumab antibody; NRS = Numeric Rating Scale; PASI = Psoriasis Area and Severity Index; PASI 75 = at least a 75% improvement from baseline in PASI score; PASI 90 = at least a 90% improvement from baseline in PASI score ; PASI 100 = a 100% improvement from baseline in PASI score; PSSI = Psoriasis Scalp Severity Index; Q2W = every 2 weeks; sPGA = static Physician Global Assessment; TE-ADA = treatment-emergent anti-drug antibody.

5. Study Design

5.1. Overall Design

Study I1F-JE-RHCV is a multicenter, open-label, post marketing clinical trial to evaluate the efficacy and safety of ixekizumab Q2W beyond Week 12 until Week 20 in patients with GPP and EP.

The study consists of 3 periods:

- **Period 1:** Screening Period (Visit 1) lasting from 7 to 30 days prior to Period 2 (baseline; Week 0; Visit 2)

Study investigator(s) will review patient history and screening test results to determine if the patient meets all inclusion and none of the exclusion criteria to qualify for participation in the study.

- **Period 2:** Induction Dosing Period from Week 0 (Visit 2) to Week 12 (Visit 6)

All eligible patients will be administered 160 mg ixekizumab as 2 SC injections at Week 0 (baseline; Visit 2) followed by 80 mg as 1 injection at Week 2, 4, 6, 8 and 10.

- **Period 3:** Maintenance Dosing Period from Week 12 to Week 20

Responders (GIS = 1 at Week 12) will complete the study.

Inadequate responders (GIS ≥ 2 at Week 12 and based on investigators' discretion) will continue to use ixekizumab 80 mg Q2W during Period 3. If patients show a therapeutic response (GIS = 1) with 80 mg Q2W after Week 12, the patient will complete the study. Patients who complete the study before Week 20 will have an early termination visit (ETV) instead of the original scheduled visit.

Patients discontinuing from the study treatment who have received at least 1 dose of investigational product will continue to the ETV.

Ixekizumab will not be made available after conclusion of the study to patients.

Study governance considerations are described in detail in [Appendix 3](#).

[Figure RHC.V.1](#) illustrates the study design.

[figure not shown]

Figure RHCV.1. Illustration of study design for Clinical Protocol I1F-JE-RHCV.

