Study I1F-JE-RHCV is a multicenter, open-label, post marketing clinical trial to evaluate the efficacy and safety of ixekizumab Q2W beyond Week 12 until Week 20 in patients with GPP and EP.

Treatment Arms and Duration:

Study I1F-JE-RHCV consists of 3 periods: a screening period of up to 30 days, a 12-week Induction Dosing Period, and an 8-week Maintenance Dosing period. All eligible patients will be administered 160 mg ixekizumab as 2 SC injections at Week 0 (baseline; Visit 2) followed by 80 mg as 1 injection at Week 2, 4, 6, 8 and 10. Patients who are inadequate responders (Global Improvement Score [GIS] ≥ 2 at Week 12 and based on the investigators' discretion) will be administered 80 mg as 1 injection at Week 12, 14, 16, and 18 or until they achieve a GIS score of 1.

Number of Patients:

A total of 12 patients will be enrolled so that at least 5 patients with EP and 5 patients with GPP who are inadequate responders (GIS ≥ 2 at Week 12 and based on the investigators' discretion) will continue to use ixekizumab beyond Week 12. Additional enrollment may occur and sample size may be increased, if no GPP or EP patients enter into Period 3 (Maintenance Dosing Period) of the study.

Statistical Analysis:

Primary analysis of efficacy, health outcome and safety measures will be conducted based on patients who continued ixekizumab 80 mg Q2W beyond Week 12 by disease type (ie, GPP and EP separately).

Baseline is defined as the last available value before the first dose in Period 2; in most cases, it will be the value recorded at Week 0 (Visit 2).

As this is a single arm study with very small sample size, no statistical inference will be performed.

Continuous data will be summarized in terms of the mean, standard deviation, minimum, maximum, median, and number of observations. Categorical data will be summarized as frequency counts.

2. Schedule of Activities

Table RHCV.1. Schedule of Activities

| Procedure | Screening Period (Period 1) | Treatment Period - Induction (Period 2) | | | | | Treatment Period - Maintenance (Period 3) | | | | ETV |
|---|-----------------------------|---|---------|---------|---------|---------|---|----------|----------|----------------|----------------|
| | V1 | V2 | V3 | V4 | V5 | V6 | V7 | V8 | V9 | V10 | |
| Study Week | - | 0 | 2 | 4 | 8 | 12 | 14 | 16 | 18 | 20 | |
| Visit Intervals | -30d to -7d | 0 | 14 ± 2d | 28 ± 4d | 56 ± 4d | 84 ± 2d | 98 ± 2d | 112 ± 2d | 126 ± 2d | 140 ± 2d | NA |

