Investigators are not obligated to actively seek AEs or SAEs in patients once they have discontinued and/or completed the study (the patient disposition CRF has been completed). However, if the investigator learns of any SAE, including a death, at any time after a patient has been discharged from the study, and he/she considers the event reasonably possibly related to the study treatment or study participation, the investigator must promptly notify Lilly.

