## **6.9. Treatment Compliance**

Throughout treatment periods, enrolled patients will record information in a Study Drug Administration Log (captured in the *Exposure as Collected* eCRF page), including the date, time, and anatomical location of administration of investigational product, package number, who administered the investigational product, and the reason if the investigational product was not fully administered.

Treatment compliance for each patient will be calculated as:

$$\text{Treatment compliance (\%)} = 100 \times \frac{\text{Total number of injections administered}}{\text{Total number of injections prescribed}}$$

- For patients who complete Period 2, the number of injections prescribed (that is, expected) during Period 2 will be equal to 7 (2 injections at Week 0 and 1 injection every 2 weeks from Week 2 to Week 10).
- For patients who discontinue during Period 2, the number of injections prescribed during Period 2 can be derived from the IWRS study drug dispense dataset.
- For patients who complete Period 3, the number of injections prescribed (that is, expected) during Period 3 will be equal to 4 (1 injection every 2 weeks from Week 12 to Week 18).
- For patients who discontinue during Period 3 or who complete study treatment because of GIS = 1 (i.e., Responder) before Week 18, the number of injections prescribed during Period 3 can be derived from the IWRS study drug dispense dataset.
- The total number of injections administered will be derived using the response to the question “Was dose administered?” on the *Exposure as Collected* eCRF page.

A patient will be considered overall compliant with study treatment if he/she misses no more than 20% of the expected doses, does not miss 2 consecutive doses (all injections at an injection week are counted as 1 dose), and does not over-dose (that is, take more injections at the same time point than specified in the protocol).

The treatment compliance (continuous variable) and the number of patients that are compliant and non-compliant (categorical variable) will be summarized for patients with GPP and EP separately and total for Period 2 and for Combined Periods 2 and 3, respectively (Analysis population: FAS Population for Period 2, Maintenance Dosing Period Population for Combined Periods 2 and 3).

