### 6.13. Safety Analyses

Safety will be assessed by AEs, laboratory analytes including neutrophil counts, vital signs, weight, and C-SSRS.

Overall AEs and treatment-emergent adverse events (TEAEs) will be summarized with frequencies. The duration of dosing exposure will also be summarized. Other safety measures will be reviewed by listings.

Summaries of overall AEs and TEAEs will be provided in patients with GPP and EP separately and total for Period 2 and for Combined Periods 2 and 3, respectively (Analysis population: FAS Population for Period 2, Maintenance Dosing Period Population for Combined Periods 2 and 3).

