#### 6.13.1. Extent of Exposure

Exposure to study drug will be summarized descriptively for Period 2 and for Combined Periods 2 and 3, respectively (Analysis population: FAS Population for Period 2, Maintenance Dosing Period Population for Combined Periods 2 and 3).

A by-patient listing of exposure duration with number of active injections and total dose will be provided (Analysis population: FAS Population).

The duration of exposure will be calculated as:

$$\begin{aligned} \text{Duration of exposure (days)} \\ &= \text{Date of last visit (scheduled or unscheduled) in Treatment Period} \\ &\quad - \text{Date of first dose in Treatment Period} + 1 \end{aligned}$$

The number of patients in each of the following categories will be included in the summaries:

- $>0, \geq 7$  days,  $\geq 14$  days,  $\geq 30$  days,  $\geq 60$  days, and  $\geq 84$  days (Period 2). Note that patients may be included in more than 1 category.
- $>0$  to  $<7$  days,  $\geq 7$  to  $<14$  days,  $\geq 14$  to  $<30$  days,  $\geq 30$  to  $<60$  days,  $\geq 60$  to  $<84$  days,  $\geq 84$  days (Period 2)
- $>0, \geq 7$  days,  $\geq 14$  days,  $\geq 30$  days,  $\geq 60$  days,  $\geq 90$  days,  $\geq 120$  days, and  $\geq 140$  days (Combined Periods 2 and 3). Note that patients may be included in more than 1 category.

- >0 to <7 days, ≥7 to <14 days, ≥14 to <30 days, ≥30 to <60 days, ≥60 to <90 days, ≥90 to <120 days, ≥120 to <140 days, and ≥140 days (Combined Periods 2 and 3).

Total dose (in mg) is calculated by the number of active injections taken during the treatment period multiplied by a dose of 80 mg.

Total number of injections received will be derived using the response to the question “Was dose administered?” on the *Exposure as Collected* eCRF page and the actual dose description from IWRS study drug dispense dataset.

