### 6.13.2. Adverse Events

Adverse events will be classified based upon the latest version of the MedDRA. Adverse events will be recorded at every study visit. Any condition starting on or after the date of informed consent will be considered an AE. Any preexisting condition which worsens in severity on or after the date of informed consent will be considered and recorded as an AE on the *Adverse Events (AE)* eCRF page from the date of worsening onwards.

A treatment-emergent adverse event (TEAE) is defined as an event that first occurred or worsened in severity after baseline and on or prior to the date of the last visit within the defined treatment period. Both the date/time of the event and the date/time of the dose (that is, injection) are considered when determining TEAEs. The TEAEs will be assigned to the study period to which it's considered treatment-emergent:

- The MedDRA lowest level term (LLT) will be used when classifying AEs as treatment-emergent.
- The maximum severity recorded for each LLT prior to the first dose date/time in the treatment period will be used as the pre-treatment severity for that LLT. If an event during the baseline period has missing severity, and the event persists during the treatment period, then it will be considered as treatment-emergent, regardless of the postbaseline level of severity. Adverse events with a missing severity during the treatment period will be considered treatment-emergent.
- Adverse events with a particular LLT will be classified as treatment-emergent if they first start on or after the first dose date/time in the treatment period (i.e., a patient has no preexisting conditions with that LLT), or if the severity is greater than the pre-treatment severity for that LLT. If a partial AE start date/time is present, the date/time will be compared as far as possible to the treatment start date/time in order to determine whether the event is treatment-emergent or not. If there is any doubt, the event will be flagged as treatment-emergent.

Overall AEs and TEAEs will be summarized for the following study periods and analysis populations:

- Period 2 (Analysis population: FAS Population)
- Combined Periods 2 and 3 (Analysis population: Maintenance Dosing Period Population).

The following summaries will be provided for Period 2 and for Combined Periods 2 and 3 (Analysis population: FAS Population for Period 2, Maintenance Dosing Period Population for Combined Periods 2 and 3):

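### No planned table shows the adverse events that arose after Week 12, or the 2 to 8 weeks of response-dependent follow-up in which they were observed

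*Protocol*

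**What the plan says.** **Exit rule.** Protocol 5.1 ends participation on response in Period 3: "If patients show a therapeutic response (GIS = 1) with 80 mg Q2W after Week 12, the patient will complete the study". The last contact is then the early termination visit: "Patients who complete the study before Week 20 will have an early termination visit (ETV) instead of the original scheduled visit".

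**Event window.** SAP 6.13.2 counts a TEAE only if it falls "on or prior to the date of the last visit within the defined treatment period". Protocol 9.2.1 adds that "Investigators are not obligated to actively seek AEs or SAEs in patients once they have discontinued and/or completed the study", although an SAE that the investigator learns of later and considers reasonably possibly related must still be notified.

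**Adverse event tables.** Protocol 10.3.4 plans one overall summary for Period 2 and one for Period 3, and protocol 10.3.1 sets the Period 3 safety baseline just before the first Period 3 dose. SAP 6.1 openly departs from this: the Maintenance Dosing Period Population is analysed over Combined Periods 2 and 3 with the Week 0 baseline. In SAP 6.13, "Overall AEs and treatment-emergent adverse events (TEAEs) will be summarized with frequencies". No rate is planned.

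**Exposure.** SAP 6.13.1 says: "Exposure to study drug will be summarized descriptively for Period 2 and for Combined Periods 2 and 3, respectively". It also lists exposure duration, injections and total dose by patient, and SAP 6.13.2 lists all adverse events by patient.

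**The concern.** Under the exit rule, the time over which a patient's post-Week 12 events can be seen depends on efficacy. At the same underlying event rate, a group that resolves early yields fewer counted events than one that does not. A low count could then mean good tolerability or short observation, and the planned tables do not separate the two.

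The combined table adds a second difficulty. It merges events from the 12-week induction, which every patient received, with events under continued Q2W, which is what the study set out to describe. Subtracting the Period 2 table does not recover the difference. That table is on the FAS, which includes patients who never entered Period 3, and a patient with events in both periods is counted once in the combined table.

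The SAP does allow for early responders in SAP 6.9, where their expected injections are taken from the dispensing data instead of the fixed four. It makes no such allowance for adverse events.

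**Working it through.** **1. The plan's own figure.** For a patient who completes Period 3, SAP 6.9 gives the expected injections "during Period 3 will be equal to 4 (1 injection every 2 weeks from Week 12 to Week 18". Weeks 12, 14, 16 and 18 make 4, so the figure is reproduced.

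**2. Length of Period 3 follow-up.** The protocol's Schedule of Activities puts the Week 12 to Week 20 visits at "84 ± 2d | 98 ± 2d | 112 ± 2d | 126 ± 2d | 140 ± 2d".
- Never resolved: 140 − 84 = 56 days = 8 weeks.
- Resolved at Week 14: 98 − 84 = 14 days = 2 weeks.
- With the ±2-day windows: 10 to 18 days at the short end, 52 to 60 at the long end.
- From Week 0, as in the SAP's combined table: 14 to 20 weeks. The shortest is 14/20 = 70% of the longest, against 2/8 = 25% for Period 3 alone.

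These ranges cover patients who leave on response or complete; other dropouts may be shorter.

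**3. Size of the effect.** The documents give no TEAE rate. Assume a constant hazard h per patient-week and 5 continuing patients in one disease group, k of whom resolve at Week 14 while the rest stay to Week 20.
- P(at least one TEAE by t weeks) = 1 − exp(−h·t).
- At h = 0.05: t = 2 gives 0.095, t = 8 gives 0.330, t = 14 gives 0.503, t = 20 gives 0.632.
- Combined patient-weeks = 14k + 20(5 − k). Expected patients with a TEAE, combined = 0.503k + 0.632(5 − k).
- The Period 3 columns use 2 and 8 weeks, with 0.095 and 0.330.

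| k of 5 | Period 3 patient-weeks | Patients with TEAE, Period 3 | Combined patient-weeks | Patients with TEAE, combined | Combined, relative to k = 0 |
|---|---|---|---|---|---|
| 0 | 40 | 1.65 | 100 | 3.16 | – |
| 1 | 34 | 1.41 | 94 | 3.03 | 4% lower |
| 2 | 28 | 1.18 | 88 | 2.90 | 8% lower |
| 3 | 22 | 0.94 | 82 | 2.77 | 12% lower |

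If all 5 left at Week 14, the combined figure would be 2.52 (20% lower). Expected events are h × patient-weeks, so events per patient-week stay at 0.05 in every row.

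**4. Sensitivity to the assumed hazard.** The reduction in the combined count is (k/5) × (1 − P14/P20). For k = 1 to 3:
- h = 0.02 (0.244 and 0.330): about 5% to 16%
- h = 0.05 (0.503 and 0.632): about 4% to 12%
- h = 0.10 (0.753 and 0.865): about 3% to 8%
- h = 0.20 (0.939 and 0.982): about 1% to 3%

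**5. Do the exposure bands show exit time?** Only partly. Duration is last visit − first dose + 1. Week 14 and Week 16 exits give 99 and 113 days, both in the 90-to-under-120 band. A Week 18 exit (127 days) shares the 120-to-under-140 band with a patient who attends Week 20 two days early (139 days). The bands are not cross-classified with events.

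**The case against.** A reader might infer that the safety counts are distorted on the scale of 2 against 8 weeks. With 3 of 5 patients resolving at Week 14, a Period 3-only count would be 0.94 against 1.65, or 43% lower. The documents do not support that reading of the SAP, because its table runs from Week 0. In the same example the count there is 12% lower, or 0.39 of a patient. Three of five resolving within two weeks is also a demanding scenario: in the earlier study cited for sample size, 2 of 13 patients had reached GIS = 1 at Week 12. That is a different setting, but it is the only response figure given.

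A reader might also infer that person-time is missing. It is not. Combined-period exposure is summarised, and exposure and events are listed by patient. With about 10 continuing patients, matching them by hand is feasible, and a rough Period 3 total could be backed out of the combined mean duration.

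Finally, the regimen under study is Q2W until GIS = 1 or through Week 18, so counts of patients with events describe that regimen as given. There is no comparator and no inference.

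All of this stands, and it limits the size of the point. It does not supply what is absent: a table of events that began or worsened after Week 12, set beside the time at risk for them.

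**Conclusion.** The point holds as a gap in presentation, and closing it is a cheap improvement. Period 3 follow-up depends on response (about 2 to 8 weeks), events after exit are not actively sought, and the SAP drops the protocol's Period 3 adverse event summary without tabulating Period 3 exposure. The safety of Q2W beyond Week 12 can therefore be read only by hand from listings.

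The effect on the counts the SAP will report is modest: about 4% to 12% lower at an assumed 0.05 TEAEs per patient-week with 1 to 3 of 5 patients resolving at Week 14, and about 1% to 16% across hazards of 0.02 to 0.20. These figures rest on a constant hazard and on resolution at the earliest scheduled visit; later resolution makes them smaller. The documents do not support reading this as a biased safety conclusion.

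**What to change.** - **SAP 6.13.1:** add Period 3 patient-weeks, from first Period 3 dose to last visit, by disease and total.
- **SAP 6.13.2:** for the Maintenance Dosing Period Population, add a summary of TEAEs, SAEs and AESIs with onset or worsening in Period 3, as protocol 10.3.4 planned, judged against the state just before the first Period 3 dose. Show patients with events, number of events, Period 3 patient-weeks and events per patient-week.
- **Combined table:** keep it and show its own patient-weeks (Week 0 onward), so that Week 0 to 20 events are never set against Period 3 time.

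**Cost:** a few lines of SAP text and some extra table columns from dates already collected, with no change to conduct. With about 5 patients per disease the rates will be unstable, and they assume a constant hazard, so the SAP should label them descriptive only.
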